treatment as usual with their regular provider(s). Individuals who meet eligibility criteria will have a 30 day run-in period in which their medication adherence will be measured with TRQ and MEMS but without an additional intervention. Following the run-in period, Stage 1 of the iTAB-CV intervention will be introduced. A member of the study team will conduct an interview in order to customize iTAB-CV for each participant at the baseline session. In the first month of iTAB-CV, participants will receive alternating daily texts with psychoeducational and motivational content once daily and a daily mood rating request to both monitor their mood and to determine engagement with the iTAB-CV intervention. In the second stage of iTAB-CV, participants will receive daily texts which will include medication reminders, contextual cues, and immediate reinforcement for medication taking behavior in addition to the content from stage 1. Assessments that include evaluation of treatment adherence, psychiatric symptoms, self-efficacy for medication taking behavior, illness beliefs, medication attitudes, and habit strength for both antihypertensive and BD medications will be conducted at four time points over a 3-month time period (screening, baseline/week 4, week 8, and week 12). Blood pressure will be measured at each of the four contacts. Individuals who drop out of the intervention, and who agree, will be followed up with outcomes assessments over the same 3-month time period that they would have been evaluated had they remained in the study.

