### **Specific Procedures:**

In phase 2, all eligible participants will receive iTAB-CV. After providing informed consent, all participants will undergo screening followed by a 30-day run-in period in which adherence will be measured using eCAP and self-report. During the 30-day run-in period, participants will continue to receive care as usual and serve as their own control with no intervention. Participants will be provided with the eCAP device for the antihypertensive agent that is missed most often. In the case of more than one such agent, the antihypertensive dosed most often. If there is again more than one such agent, the most recently prescribed agent will be chosen. Based on our experience with MEMs, the Hawthorne effect wears off after 1-2 weeks. After the 30-day run-in period, participants will receive 30 days of stage one of iTAB-CV. The study PI or study staff will conduct an interview in order to customize iTAB-CV for each participant at the baseline session.

In stage one of iTAB-CV, participants begin receiving 1 daily educational/motivational customized text messages addressing medication attitudes, social influences, and self-efficacy which will alternate between antihypertensives and BD medications without reminders and 1 daily mood rating. Participants will identify any stems that they don't want to receive and can write in their own personalized messages. At the 8 week meeting, the study PI or study staff will conduct a brief 2nd iTAB-CV interview to determine the types of medications taken (antihypertensives and/or bipolar medications) and at which times of day as well as to pick reminders/reinforcement texts that the participant wants to receive for stage two.

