**b. eCAP:** Study participants will be given an eCAP device for one of their pill bottles, which will record time/date of bottle opening. eCAP will be used for the antihypertensive medication that the patient missed the most frequently in the past week (in the case of multiple antihypertensive medications missed the same proportion of times, the medication dosed most often will be chosen). This method was chosen over monitoring all medications to limit burden, and is appropriate since eCAP is used to confirm the TRQ. A dose will be counted as “taken” if the bottle is opened within six hours of the prescribed time. We will calculate a percent of doses taken by dividing the number of times the bottle is opened by the number of times it should have been opened as per the prescription. Participants who use organizers rather than bottles will be instructed to open and then shut an empty bottle with an eCAP as a “diary” each time they open their pill organizers. Participants will be given the eCAP at the screening visit if they fit inclusion/exclusion criteria. eCAP will be assessed at the baseline visit based upon pill-taking behavior during the interval between screening and baseline visit. Baseline visits will be targeted at 4 weeks after completion of the screening visit. At screening, participants will be asked when their index drug is up for a refill. They will then be reminded to refill their index drug and fill their eCAP via the iTAB-CV system.

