**Compensation for research participation:**

To help cover their costs and reimburse them for their time and effort, each subject will be compensated \$40 for the screening visit and \$30 for each of the remaining three assessments: baseline (4 weeks), visit 1 (8 weeks), and visit 2 (12 weeks). Additionally, participants will receive \$10 for bringing the eCAP to each of the baseline, 8 week, and 12 week visits. Participants will be given bus or parking passes with approximately a \$5 value for transportation for each assessment if needed. Each participant for phase 2 will potentially receive a total of \$160 plus \$20 for transportation if needed. Participants will either be paid by a check mailed to them or petty cash. Transportation reimbursement will be given in the form of a bus pass, a parking voucher, or in rare cases, cash at the time of the visit. Participants will also be able to keep the cell phones provided to them at baseline and unlimited texting from baseline until their completion in the study.

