**Table 1: Schedule of Assessments and Study Events**

Procedure	Screen	Baseline	Visit 1	Visit 2
Visit Timing	Day 0	Week 4	Week 8	Week 12
Informed Consent	X			
Inclusion/Exclusion	X			
Demographics, Charlson, medical history	X			
Diagnosis: Mini-International Neuropsychiatric Interview	X			
Prospective Memory: The Memory for Intentions Screening Test (MIST)	X			
Rapid Estimate of Adult Literacy in Medicine – Short Form (REALM-SF)	X			
Brief Illness Perception Questionnaire (Brief IPQ)	X		X	X
Medication Adherence Self-Efficacy Scale - Revised (MASES-R)	X		X	X
Medication Attitudes – Beliefs About Medicines Questionnaire, AMSQ	X		X	X
Self-Report Habit Index	X	X	X	X
Primary outcomes:				
Average TRQ for antihypertensive agents	X	X	X	X
eCAP for antihypertensive agent		X	X	X
Secondary outcomes:				
Systolic Blood Pressure	X	X	X	X
Height (Screen only) and weight / BMI	X	X	X	X
Average TRQ for bipolar medications	X	X	X	X
Brief Psychiatric Rating Scale (BPRS)	X	X	X	X
Montgomery-Åsberg Depression Rating Scale (MADRS)	X	X	X	X
Young Mania Rating Scale (YMRS)	X	X	X	X
Introduction of eCAP for antihypertensive	X			
Brief powerpoint presentation providing psychoeducation on hypertension and bipolar disorder		X		
iTAB-CV interview and training; iTAB-CV stage 1 - initiation of behavioral priming via text + daily mood monitoring; phone given at this time		X		
iTAB-CV stage 2 – brief interview regarding iTAB-CV; frequency of text; choose stems for reminders and reinforcement			X	
Participant acceptability/satisfaction/feasibility/exit interviews				X

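### Prompts to refill the index drug and fill the eCAP bottle are tied to iTAB-CV, which starts at week 4, so eCAP may be supported differently in the two periods being compared

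*Combined protocol and SAP*

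**What the plan says.** The eCAP paragraph under Adherence sets the sequence: "At screening, participants will be asked when their index drug is up for a refill". The next sentence is "They will then be reminded to refill their index drug and fill their eCAP via the iTAB-CV system". It gives no start date for these prompts.

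Three places date the start of iTAB-CV. The Overview has "Following the run-in period, Stage 1 of the iTAB-CV intervention will be introduced". Table 1 puts the iTAB-CV interview, training and stage 1 at week 4, with "phone given at this time". The compensation section refers to "cell phones provided to them at baseline and unlimited texting from baseline until their completion in the study".

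The baseline eCAP value comes from before that point: "eCAP will be assessed at the baseline visit based upon pill-taking behavior during the interval between screening and baseline visit". Specific Procedures describes this run-in as a time when participants "serve as their own control with no intervention".

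The Data Analysis plan tests the eCAP change from baseline to week 12 with a paired t-test, next to the TRQ. It calls TRQ the main adherence measure. Table 1 lists both under primary outcomes.

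**The concern.** The eCAP percentage divides bottle openings by the openings due under the prescription. No rule covers days when the participant took the drug from another container, such as a new pharmacy bottle after a refill. Those days score as missed doses. The eCAP-fill prompt guards against this, and as the plan reads, the guard is in place only from week 4.

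The baseline and week-12 values would then be recorded under different conditions. Participants are their own controls, so no parallel arm cancels the difference. At stake is the reading of the only electronic adherence measure, which the plan uses to confirm the self-report. The planned TRQ-eCAP correlations and Bland-Altman plots would be affected too. The plan says its estimates will inform a later controlled trial, so an artefact could carry forward.

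**Working it through.** **Timing: two readings.**
- Prompts start at week 4. This fits the Overview, Table 1 and the compensation section. The run-in then has no such prompts and the later intervals do.
- Prompts start at screening. This fits the fact that the refill date is asked then. But iTAB-CV would be running before the phone is issued, in a period described as having no intervention.

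Either way the sections need reconciling. The calls or texts in the two weeks before a visit (Specific Procedures) are appointment reminders and are not said to cover refills or the eCAP.

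**The two prompts differ.** A prompt to fill or use the eCAP bottle acts on measurement: it can raise recorded openings with no more doses taken. A refill prompt can raise true adherence, and its effect is then not an artefact.

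**The plan's own figure.** Inputs from the power analysis: 38 participants, 25% attrition, effect size 0.549, two-sided alpha 0.05. Completers: 38 × 0.75 = 28.5. The exact noncentral-t power of a paired t-test is 0.7997 with 28 completers and 0.814 with 29. The stated 0.80 is reproduced. It concerns TRQ and does not change here.

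**Illustration of size.** The documents give neither the share of participants affected nor the days lost. Assume that 20% of bottle users lose 7 recorded days of a 28-day run-in and none later.

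Artefact in points = 100 × share × (days lost / 28) × underlying adherence on those days.

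Rejection probability when true adherence does not change: two-sided paired t-test at 5%, 28 completers, standardised shift = artefact / 39. The SD of 39 comes from the TRQ power analysis and is borrowed for eCAP.

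| Underlying adherence (assumed) | Artefact | Shift | Rejection probability |
|---|---|---|---|
| 100% (upper limit) | 100 × 0.20 × 7/28 = 5.0 points | 5.0/39 = 0.128 | 0.100 |
| 80% | 5.0 × 0.8 = 4.0 points | 4.0/39 = 0.103 | 0.082 |
| 50% | 5.0 × 0.5 = 2.5 points | 2.5/39 = 0.064 | 0.062 |

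The lower rows matter because entry requires at least 20% of an antihypertensive to be missed, and the eCAP goes on the most-missed agent. Against the 21.7-point change used for planning, the three artefacts are 23%, 18% and 12%.

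**The opposing effect.** Specific Procedures says that reactivity to monitoring fades after 1 to 2 weeks, which lies inside the run-in. If it raised recorded adherence by 5 to 20 points (assumed) for 1 to 2 of 4 weeks, baseline eCAP would be too high by between 5 × 1/4 = 1.25 and 20 × 2/4 = 10 points. That shrinks the apparent gain.

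**The case against.** A reader might infer that the eCAP gain is inflated, or that any artefact must favour the intervention. The documents do not support that. They give no frequency or length of gaps in eCAP use, they leave the start of the prompts unstated, and they describe a reactivity effect in the opposite direction. The net direction cannot be fixed. That part of the case against stands.

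Four further limits stand:
- Missed openings because the drug was not refilled are real missed doses. Improvement from a refill prompt is not a false positive.
- Pill-organizer users open an empty eCAP bottle by design, so filling it does not apply to them.
- TRQ is the main and powered measure, and this mechanism does not act on it directly. The study is an uncontrolled pilot.
- Prompts in the run-in could themselves raise the baseline, so extending them is not free of side effects.

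A reader might also see a contradiction in the stage-one description, "which will alternate between antihypertensives and BD medications without reminders and 1 daily mood rating". The contrast there is with the medication-taking cues and reminders of stage two, and a refill prompt is a different message. I place no weight on it.

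What the objection does not remove is the asymmetry. An opposing bias of unknown size does not repair this one, and no reading of the timing makes the sections agree.

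**Conclusion.** The point holds as a possible bias and an unresolved timing question. If the prompts begin with iTAB-CV at week 4, the compared periods have different eCAP support, and this mechanism alone may push the eCAP change upward. Under the illustrative gap, the shift is 2.5 to 5.0 points and the rejection rate about 6% to 10% instead of 5%. Those figures rest on assumed gaps and adherence levels, a borrowed SD, 28 completers and no loss after baseline. They are not estimates for this trial. The TRQ analysis stands as planned. This is a cheap improvement.

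**What to change.** 1. Reconcile Specific Procedures, the eCAP paragraph and Table 1 on when the refill and eCAP-fill prompts start.
2. Give the eCAP-use prompt by the same route and frequency in all three 4-week intervals from screening, outside iTAB-CV and within the between-visit contacts already planned. For organizer users, the prompt is the instruction to open the empty eCAP bottle.
3. State whether the refill prompt is part of the intervention or a measurement aid. If it is an aid, give it equally in all intervals.
4. At each visit, record the days on which the index drug was taken from a container other than the eCAP bottle. Organizer users who follow the diary instruction are not counted here.
5. Repeat the eCAP comparison with only those days excluded, in every interval. Keep days without any drug as missed doses, since dropping all empty-bottle days would delete real non-adherence.

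The cost is one short contact per participant in the run-in, one data field and one sensitivity analysis. The extra contact may slightly raise baseline recording.

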#### **BD Symptoms:**

- a. **Brief Psychiatric Symptom Scale (BPRS):** The BPRS is a clinician rated measure that evaluates the spectrum of symptoms seen in individuals with BD (including mania, psychosis, depression and disorganization) (Shafer, 2005).
- b. **Montgomery Asberg Depression Rating Scale (MADRS)** (Montgomery & Asberg, 1979): The MADRS measures symptoms of depression. Total scores on MADRS range from 0-60, with higher scores indicating more severe depression.
- c. **Young Mania Rating Scale (YMRS):** The YMRS is a clinician rated measure of mania symptoms. Irritability, speech, thought content, and disruptive/aggressive behavior are doubly weighted and are rated on a 0 to 8 scale. The remaining 7 items are rated on a 0 to 4 scale (Martha Sajatovic et al., 2015).

**Additional Measures:**

- a. **Health resource use in the 3-month period prior to study enrollment and in the 3-month study period (emergency care, hospitalization, outpatient mental health and primary care/other medical care visits)**
- b. **Charlson Comorbidity Index (CCI):** Self Report Version - Data on comorbid medical conditions will be collected based on the self-report version of the CCI (Charlson, Pompei, Ales, & MacKenzie, 1987; Chaudhry, Jin, & Meltzer, 2005). The CCI summary score is comprised of the presence of 10 medical conditions including respiratory diseases, rheumatological diseases, cancer, diabetes, digestive problems, heart trouble, HIV or AIDS, kidney disease, liver disease, and stroke. While the original CCI includes dementia, it was excluded from the self-report version given that those with dementia would not be able to provide informed consent. Each disease category is assigned a weight which represents mortality risk with lower scores indicative of lower risk.
- c. **Mini-International Neuropsychiatric Interview 7.0.2.(MINI):** The MINI is a diagnostic interview which takes approximately 15 minutes to administer and is based on the DSM and ICD psychiatric disorders (Sheehan et al., 1998).
- d. **Medical history**
- e. **The Memory for Intentions Screening Test (MIST):** The MIST is a task-oriented measure for prospective memory and takes approximately 30 minutes to administer. This multidimensional task analyzes the skills used to complete the eight tasks that make up the test, and is appropriate for those with neurological disorders (Woods et al., 2008).
- f. **Rapid Estimate of Adult Literacy in Medicine –Short Form (REALM-SF):** The REALM-SF is a 7 item measure that identifies patients that are at high risk for having limited health literacy. The measure is quick, taking only a minute or two, and identifies the grade level of the patient if they read below the ninth grade level (Davis et al., 1993).
- g. **Brief Illness Perception Questionnaire (Brief IPQ):** The Brief IPQ is a nine item paper and pencil questionnaire that provides a quick assessment of illness perceptions. Each item is rated on a five-point Likert scale (Broadbent, Petrie, Main, & Weinman, 2006).
- h. **Medication Adherence Self-Efficacy Scale - Revised (MASES-R):** The MASES-R is a 13 item questionnaire that measures patient's confidence to adhere to their antihypertensive medication regimen under various challenging conditions. The total score ranges from 1-4 and is the average score of all 13 items. Higher scores are indicative of higher self-efficacy (Fernandez, Chaplin, Schoenthaler, & Ogedegbe, 2008).
- i. **Self-Report Habit Index (SRHI):** The SRHI is a 12 item self-report questionnaire that measures habit strength and will be administered regarding the habit of taking medication (Verplanken & Orbell, 2003).
- j. **Blood Pressure:** Systolic and diastolic blood pressure will be taken with an automatic blood pressure monitor at each study visit.
- k. **Height and Weight/BMI:** Height will be measured at the screen visit and weight will be taken at each visit so BMI can be calculated.

**Medication Attitudes Measures:**

- a. **Beliefs About Medicines Questionnaire (BMQ):** The BMQ is an 18-item measure split into two sections, one for beliefs regarding medication in general and one for beliefs about an individual's own prescribed medications (Horne, Weinman, & Hankins, 1999; Ruppap, Dobbels, & De Geest, 2012).
- b. **Attitude toward Mood Stabilizers Questionnaire (AMSQ):** A modification of the Lithium Attitudes Questionnaire, the 19-item AMSQ evaluates an individual's attitudes towards psychiatric medication (Chang, Sajatovic, & Tatsuoka, 2015).

**Clinician involvement:**

Individual iTAB-CV interviews will be administered by the study PI or by a trained research team member. Clinician buy-in remains important. Providers will be encouraged to refer patients they believe are sub-optimally adherent.

Providers will be notified of participant enrollment in the study.

**Risks associated with study participation:**

This study involves completing a set of self-report instruments, along with rating interviews and an intervention customization interview. All of these instruments have been utilized in outpatient research settings and are not associated with risks to patients. The iTAB-CV intervention to enhance treatment adherence involves the use of cognitive and behavioral strategies including psychoeducation, motivational interviewing, context cues/reminders, and positive reinforcement all delivered via text messaging.

The risks to the subjects will be primarily those of talking about some matters, which they may find uncomfortable. Participants do not have to answer upsetting questions, and may discontinue the interview if they wish. It is also possible that the intervention will have no effect on treatment adherence and that receiving texts may become an annoyance. Participants have the option of not responding to texts. They can also stipulate times of the day during which they don't want to receive texts.

Furthermore, the text messages will query regarding daily mood ratings. These approaches are not generally known to increase risk to individuals. Individuals with bipolar disorder are already at risk for depression and possible suicidality. While this intervention is unlikely to increase these risks, it may be able to detect them more readily given the daily mood ratings. There is an automated texting sequence to address texts indicating severely low or high mood which will provide the participant with information on how to access immediate emergency services. If there are 3 such mood ratings in a row, an automatic text will be sent to the research assistant who will follow up by phone with the participant.

The study requires that participants receive medication reminders to take medications as well as answer daily questions about their mood on their mobile device. If a participant chooses to store personal information on this device, it is possible that if the device were lost, the confidentiality of the participant may be compromised. It is possible that participants could put personal information on the device that could link to the delivered text messages, but the risk of losing confidential information in this way is exactly the same as the risk incurred by owning and using any cellular phone. The text messages used in this study are not specific to bipolar disorder and are purposefully generic. Reminders do not use medication names but rather category of medication (high blood pressure medicine or bipolar medicine) and the mood question is generic. While participants in the patient focus groups indicated that they prefer to have the text messages use the actual name or their disorder, participants will have the option of choosing an alternative name if they wish. The text messages will be delivered from a generic phone number that will not be linked to the specific study goals.

If the phone were to be lost, persons could find responses to medication and mood queries. This will be clearly articulated to participants as a study risk and is specified in the consent document. If participants are uncomfortable with this risk, they may choose not to enroll in the study.

Participants will have their blood pressure taken 4 times over a 12-week period. There is minimal risk to blood pressure readings.

The study requires the participant to place a device on top of a standard pill bottle which may compromise the use of pill organizers or other devices to manage their medications. This may affect their medication adherence.

Participants may choose not participate in the study and this will not in any way affect their regular care with clinicians. Individuals who do choose to participate in the study will continue to receive treatment as usual from their regular care provider(s).

It is possible that the subjects' physical or mental health may worsen during their participation. Subjects will be in close communication with the research study team to make sure they are monitored for unexpected worsening and that the appropriate measures are taken.

Subjects will be free to withdraw from the study at any time without penalty. If during the course of the assessment, the subject communicates to the rater or investigator that the subject may be in immediate danger or at acute risk of harm to self or others, (for example, reporting a suicide plan), the study staff interacting with the individual will immediately notify 1) The patient's clinician and 2) The study PI so that all available and appropriate measures may be taken to ensure the prompt safety and most appropriate care setting for the patient. If at any point a subject presents with what are deemed to be unsafe blood pressure readings (i.e.  $\geq 170$ mg Hg), the study PI, psychiatrist-investigator or internist-investigator will be notified. The study staff will notify the subject's clinician and accompany them to the ER if it is deemed necessary.

